2.8.4 Vital signs

Week 24 analysis

For vital sign data collected during Epoch 3, descriptive statistics will be provided for absolute values and change from baseline at each assessment time point by treatment group as appropriate.

The number and percentage of patients with newly occurring or worsening notable values, including notable change from baseline will be summarized by vital sign parameter at each

assessment time point by treatment group. Notable absolute values and notable changes from baseline for each vital sign parameter are defined in Table 2-6 and Appendix 1 of the protocol. A listing of all patients with notable vital sign values and changes will be provided.

End of study analysis

Similar analysis to that done at Week 24 will be conducted for the end of study analysis for vital sign data collected during Epoch 4.

Table 2-6 Vital signs notable range deviations

Vital signs		Notable abnormalities
Pulse (beats/min)		either ≥ 120 + increase $\geq 25^*$ or > 130 either ≤ 50 + decrease $\geq 30^*$ or < 40
BP (mmHg)	systolic	either ≥ 180 + increase $\geq 30^*$ or > 200 either ≤ 90 + decrease $\geq 30^*$ or < 75
	diastolic	either ≥ 105 + increase $\geq 20^*$ or > 115 either ≤ 50 + decrease $\geq 20^*$ or < 40

* Refers to post-BL value as compared to BL value.

2.8.5 ECG

The following quantitative variables will be summarized: QTcF duration (msec), Heart rate (beats/min), PR duration (msec), RR duration (msec), and QRS duration (msec).

Week 24 analysis

Changes from baseline for ECG variables will be provided; for QTcF and heart rate, inferential statistics will be generated as well.

The number and percentage of subjects with the following criterion will be presented.

- QTcF > 500 msec
- QTcF > 480 msec
- QTcF > 450 msec
- QTcF increases from baseline ≥ 30 msec
- QTcF increases from baseline ≥ 60 msec
- PR > 200 and ≤ 220 msec
- PR > 220 msec
- PR increases from baseline $> 25\%$ and to a value > 200 msec
- QRS > 110 and ≤ 120 msec
- QRS > 120 msec
- QRS changes from baseline $> 25\%$ and to a value > 110 msec

- Heart rate > 100 beats/min
- Heart rate < 50 beats/min

In addition, shift tables comparing baseline ECG results (normal, abnormal, not available, total) with the maximum on-study result (normal, abnormal, not available, total) will be provided for each variable.

Cutoff points below are used to define normal or abnormal criteria:

- QTcF: >450 or = <450 msec for male and >460 or = <460 msec for female
- QRS: >120 or = <120 msec
- PR: >200 or = <200 msec
- HR: >100 or = <100 beats/min

A listing of ECG parameters together with newly occurring or worsening abnormalities will be provided.

End of study analysis

Similar analyses outlined for Week 24 will be provided for the End of study analysis.

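### The ECG shift table has no lower heart-rate limit, so a new rate below 50 beats/min is tabulated as normal unless the subject also has a value above 100

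*SAP*

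**What the plan says.** SAP 2.8.5 (ECG) contains four relevant outputs for Week 24 and asks for similar ones at end of study.

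- **Counts.** "The number and percentage of subjects with the following criterion will be presented"; the list that follows includes both "Heart rate > 100 beats/min" and "Heart rate < 50 beats/min". The section calls these criteria; the term notable belongs to the vital-signs and laboratory sections.
- **Shift tables.** The plan is for "shift tables comparing baseline ECG results (normal, abnormal, not available, total") to be set against the post-baseline period, "with the maximum on-study result (normal, abnormal, not available, total) will be provided for each variable".
- **Classification.** "Cutoff points below are used to define normal or abnormal criteria". For heart rate the only entry is "HR: >100 or = <100 beats/min".
- **Listing.** "A listing of ECG parameters together with newly occurring or worsening abnormalities will be provided". No separate definition of abnormality is given for it.

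Two other places bear on the point. The laboratory shift tables in SAP 2.8.3 use the most extreme value after baseline (or after Week 24), not the maximum. The pulse rule in SAP Table 2-6, identical to protocol Table 13-1, flags a low pulse if it is at or below 50 with a fall of at least 30 from baseline, or below 40.

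**The concern.** Section 2.8.5 treats both a high and a low heart rate as worth counting, but its shift table can register only the high side. With one upper cut-off, a rate of 45 falls in the same class as 70. Taking the maximum compounds this, because for a low-side change the maximum is the least abnormal value on study.

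Heart rate is the only ECG variable for which this matters. QTcF, PR and QRS have only high-side criteria in the section, so an upper cut-off and the maximum suit them. They also each have a criterion tied to baseline, whereas heart rate has none. RR duration is summarised but has no cut-off, so it cannot show the low side of heart rate in another form.

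What is at stake is the ability to read from one ECG table, by dose, how many subjects newly developed a heart rate below 50. Cardiotoxicity is on the pre-defined list of special-interest issues in SAP 2.8.1.1. Protocol 3.6 also notes that SGLT1 is expressed in the heart and that its function there is poorly understood.

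**Working it through.** The plan gives no figure to reproduce. The check applies the stated rule to made-up heart-rate series and compares it with the section's own limits. None of these series is trial data.

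**Inputs**

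- Shift cut-off: above 100 versus 100 or below (SAP 2.8.5). The SAP does not say which side is abnormal. I take above 100 as abnormal, by analogy with the QTcF, QRS and PR cut-offs and the count above 100.
- Post-baseline value: maximum on study (SAP 2.8.5).
- Low and high criteria: below 50 and above 100 (SAP 2.8.5).
- Alternative summary value: most extreme (SAP 2.8.3).
- Pulse rule: SAP Table 2-6.

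**Step 1. Rules**

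- SAP rule: class(x) = abnormal if x > 100, otherwise normal. Table cell = class(baseline) to class(maximum on study).
- Two-sided rule: class(x) = abnormal if x < 50 or x > 100, otherwise normal. It is applied first to the maximum, then to the most extreme value (abnormal if any on-study value is abnormal).

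**Step 2. Results**

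| Baseline; on-study values | SAP rule | Two-sided, maximum | Two-sided, most extreme | In <50 count? |
|---|---|---|---|---|
| 70; 72, 45, 68 | normal to normal | normal to normal | normal to abnormal | yes |
| 70; 45, 46, 44 | normal to normal | normal to abnormal | normal to abnormal | yes |
| 70; 45, 104 | normal to abnormal | normal to abnormal | normal to abnormal | yes |
| 46; 60, 62 | normal to normal | abnormal to normal | abnormal to normal | no |
| 70; 105 | normal to abnormal | normal to abnormal | normal to abnormal | no |

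Row 1 shows that a lower limit alone is not enough when on-study values vary: the maximum is 72, and the drop to 45 stays hidden. Row 2 shows that the lower limit is enough when every on-study value is low. Row 3 is the exception: the subject is classed abnormal, but because of 104, not 45. Row 4 shows that a low baseline is also classed as normal.

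**Step 3. A different reading of the maximum result.** If it means the worst category instead of the largest number, rows 1 and 2 remain normal to normal under the SAP cut-off, because every value of 100 or below is one class.

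**Step 4. Does the pulse rule fill the gap?** For 70 falling to 45, the fall is 70 - 45 = 25, which is less than 30, and 45 is not below 40. The rule does not flag it. At a pulse of 45 the rule needs a baseline of at least 45 + 30 = 75.

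**Step 5. Does the <50 count fill it?** The criterion has no baseline condition. A subject at 48 both before and during treatment could count the same as one who fell from 70 to 45.

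**The case against.** The strongest reply is that low heart rate is already well covered. Section 2.8.5 counts rates below 50, gives changes from baseline with inferential statistics for heart rate, and summarises RR. SAP 2.8.4 tabulates new or worsened notable pulse, including low pulse, at each time point. Protocol 6.5.4 has clinically significant ECG abnormalities recorded on the medical history or AE forms, and special-interest events, cardiotoxicity among them, are summarised by treatment. On this view the shift table is a deliberate upper-limit display: all four cut-offs are upper limits, the maximum matches them, and low rates have their own row. Randomisation also makes the <50 counts comparable with placebo on average.

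Much of this stands. What is missing is one cross-tabulation, and a between-arm difference in the <50 count remains interpretable, though noisier than a baseline-linked count in arms of about 36. It does not remove the gap: group-level changes do not identify who newly fell below 50, the pulse rule is stricter, and the listing is not a summary by treatment. If the listing uses the shift-table cut-offs, it misses these subjects too.

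The point about the maximum is conditional. It matters only if a subject has more than one post-baseline ECG in the analysis period, and the ECG row of Table 6-1 could not be read in the text available. With a single ECG, minimum and maximum coincide. The missing lower limit does not depend on this.

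A reader might infer more than the documents support:

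- *That low heart rates go unreported.* They do not; the <50 row reports them.
- *That every new low rate is misclassed.* A subject who also exceeds 100 is shown as abnormal, though for the high value.
- *That a number of affected subjects can be stated.* The documents give no rate of on-study heart rate below 50.
- *That a known cardiac effect is being hidden.* No section names low heart rate as a known or suspected effect, and protocol 3.6 describes 150 mg qd as safe and well tolerated in studies of up to 12 weeks.

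**Conclusion.** The inconsistency is real but minor. As written, a heart rate below 50 cannot by itself produce an abnormal entry in the ECG shift table, although the same section treats it as a criterion to be counted. Consequently no ECG summary table shows new-onset heart rate below 50 by treatment, at Week 24 or at end of study.

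The conclusion assumes that above 100 is the abnormal side. The added effect of using the maximum also assumes more than one post-baseline ECG per period. The consequence is limited to a descriptive safety table, and to the abnormality listing if it shares the cut-offs. Data collection and the primary analysis are unaffected.

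**What to change.** In SAP 2.8.5:

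1. Class heart rate for the shift table as low (<50), normal (50-100) or high (>100) beats/min, which are the section's own limits.
2. Show the heart-rate shift from baseline to both the minimum and the maximum on-study value. Alternatively, use the most extreme value, as SAP 2.8.3 does for laboratory parameters. With the most extreme value, state how a subject with both a low and a high value is shown.
3. State that the listing of new or worsened ECG abnormalities uses the same limits.
4. Apply all of this to both the Week 24 and the end-of-study analysis.

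The QTcF, QRS and PR shift tables need no change on this account. The cost is a few lines of SAP text and one extra descriptive panel per analysis, with no new data.

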2.8.6 Liver events

Week 24 analysis

Liver events and laboratory trigger definitions and follow-up requirements are defined in Appendix 2 of the protocol.

The laboratory parameters for liver function will be shown in the laboratory standard tables as discussed in Section 2.8.3. In addition, summary tables will be provided on the number and percentage of subjects who meet the following liver toxicity criteria post baseline by Week 24.

Listings of patients with clinically notable LFT values will be provided.

Table 2-7 Criteria for evaluating liver toxicity

Parameter	Criterion
ALT or AST	ALT or AST > 3xULN ALT or AST > 5xULN ALT or AST > 8xULN ALT or AST > 10xULN
Hy's category	ALT or AST > 3x ULN and TBL > 1.5x ULN ALT or AST > 3xULN & TBL > 2xULN ALT or AST > 5xULN & TBL > 2xULN ALT or AST > 8xULN & TBL > 2xULN ALT or AST > 10xULN & TBL > 2xULN ALT or AST > 3xULN & TBL > 2xULN & ALP ≤ 2xULN

Parameter	Criterion
TBL&ALP	TBL >1.5x ULN and ALP >2x ULN TBL >2x ULN and ALP >2x ULN
Isolated TBL	TBL >1.5x ULN & ALT and AST \leq 3x ULN and ALP \leq 2x ULN TBL >2x ULN & ALT and AST \leq 3x ULN and ALP \leq 2x ULN TBL >3x ULN & ALT and AST \leq 3x ULN and ALP \leq 2x ULN
Isolated ALP	ALP >1.5x ULN & ALT and AST \leq 3x ULN and TBL \leq 1.5x ULN ALP >2x ULN & ALT and AST \leq 3x ULN and TBL \leq 1.5x ULN ALP >3x ULN & ALT and AST \leq 3x ULN and TBL \leq 1.5x ULN ALP >5x ULN & ALT and AST \leq 3x ULN and TBL \leq 1.5x ULN

ALP: alkaline phosphatase; ALT: alanine aminotransferase; AST: aspartate aminotransferase; TBL: total bilirubin; ULN: upper limit of normal.

End of study analysis

Summary tables will be provided on the number and percentage of subjects who meet the liver toxicity criteria after Week 24 until end of the study (Epoch 4).

2.8.7 Renal events

Week 24 analysis

The overall frequency of events and percentage of patients with renal events during the treatment period will be provided for the Week 24 analysis. Furthermore, the frequency and percentage of patients with renal events during Epoch 3 will be provided by treatment and the first identified criterion. The frequency of patients with renal events and percentage will be provided for clinical signs and symptoms by the treatment.

Renal event overview data, pathology data, and imaging data will be provided in listings.

The renal function lab data will be analyzed in Section 2.8.3 Laboratory data.

End of study analysis

Similar analyses will be conducted for the End of study analysis for those patients who entered Epoch 4 of the study.

Table 2-8 Specific renal alert criteria

Criteria	Action required
Serum event	
Serum creatinine increase 25 – 49 % compared to BL	Confirm 25 % increase after 24-48h Follow up within 2-5 days
Acute kidney injury: serum creatinine increase \geq 50 % compared to BL	Follow up within 24-48h if possible Consider study treatment interruption Consider subject hospitalization /specialized treatment
Urine event	
New dipstick proteinuria \geq 1+	Confirm value after 24 to 48-h

Albumin- or protein-creatinine ratio increase ≥ 2 -fold	Perform urine microscopy
Albumin-creatinine ratio (ACR) ≥ 30 mg/g or ≥ 3 mg/mmol;	Consider study treatment interruption / or discontinuation
Protein-creatinine ratio (PCR) ≥ 150 mg/g or >15 mg/mmol	
New dipstick hematuria $\geq 1+$ not due to trauma	Urine sediment microscopy Perform serum creatinine, ACR

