**Table 6-5 Urinalysis**

Category	Parameter(s)
Urinalysis	pH, specific gravity, protein, glucose, ketones, nitrites, blood, leucocytes
Urinalysis	Urine albumin to creatinine ratio (spot urine)
Urine (dipstick)	Hematuria
Urine (dipstick)	Pregnancy test ( $\beta$ -hCG)

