## 7.4 Renal safety monitoring

The following two categories of abnormal renal laboratory values have to be considered during the course of the study:

- Serum event:
  - Confirmed (after  $\geq 24\text{-h}$ ) increase in serum creatinine of  $\geq 25\%$  compared to BL during normal hydration status.
- Urine event:
  - New onset ( $\geq 1+$ ) proteinuria; confirmed by doubling in the urinary albumin-creatinine ratio.
  - New onset ( $\geq 1+$ ) hematuria.

Every renal laboratory trigger or renal event as defined in [Table 15-1](#) in [Appendix 3](#) should be followed up by the investigator or designated personnel at the study site as summarized in [Appendix 3](#).

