## 15 Appendix 3: specific renal alert criteria and actions

**Table 15-1 Specific renal alert criteria and actions**

Criteria	Action required
Serum event	
Serum creatinine increase 25 – 49 % compared to BL	Confirm 25 % increase after 24-48h Follow up within 2-5 days
Acute kidney injury: serum creatinine increase $\geq$ 50 % compared to BL	Follow up within 24-48h if possible Consider study treatment interruption Consider subject hospitalization /specialized treatment
Urine event	
New dipstick proteinuria $\geq$ 1+ Albumin- or protein-creatinine ratio increase $\geq$ 2-fold Albumin-creatinine ratio (ACR) $\geq$ 30 mg/g or $\geq$ 3 mg/mmol; Protein-creatinine ratio (PCR) $\geq$ 150 mg/g or $>$ 15 mg/mmol	Confirm value after 24 to 48-h Perform urine microscopy Consider study treatment interruption / or discontinuation
New dipstick hematuria $\geq$ 1+ not due to trauma	Urine sediment microscopy Perform serum creatinine, ACR
For all renal events	
Document contributing factors in the eCRF (see Section 7.4 ): co-medication, other co-morbidity conditions, and additional diagnostic procedures performed.	
Monitor subject regularly (frequency at investigator's discretion) until either:	

• event resolution: serum creatinine within 10 % of BL or protein-creatinine ratio within 50 % of BL, or

• event stabilization: serum creatinine level with <math>\pm</math>10 % variability over last 6 months or protein-creatinine ratio stabilization at a new level with <math>\pm</math>50 % variability over last 6 months.

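### Protocol 7.4 and Table 15-1 (repeated as SAP Table 2-8) define the renal event differently, and two absolute urine thresholds let unchanged baseline albuminuria be counted as an event

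*SAP*

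**What the plan says.** Protocol 7.4 names two kinds of renal event.

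- The serum event is a creatinine rise of at least 25 % over baseline, confirmed after at least 24 hours and seen under normal hydration.
- The urine event is new proteinuria of 1+ or more, "confirmed by doubling in the urinary albumin-creatinine ratio", or new hematuria of 1+ or more.

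The same section then sends the reader to Table 15-1 in Appendix 3 for the definition of a renal trigger or event.

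Table 15-1, repeated as SAP Table 2-8, lists:

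- two creatinine levels, both relative to baseline: 25–49 % with the action "Confirm 25 % increase after 24-48h", and ≥ 50 % under "Acute kidney injury: serum creatinine increase";
- a block that opens with "New dipstick proteinuria" and continues with "Albumin- or protein-creatinine ratio increase" (2-fold or more), ACR ≥ 30 mg/g and PCR ≥ 150 mg/g;
- new dipstick hematuria.

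Table 15-1 also uses PCR to close an event: "event resolution: serum creatinine within 10 % of BL or protein-creatinine ratio within 50 % of BL". The urinalysis schedule in Protocol Table 6-5 has an albumin-creatinine ratio on spot urine but no PCR.

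SAP 2.8.7 plans counts and percentages of patients with renal events: "the frequency and percentage of patients with renal events during Epoch 3 will be provided by treatment and the first identified criterion". It gives no rule for the source of the events, for confirmation, or for how the lines of the urine block combine.

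**The concern.** Sites and programmers have two definitions of one event. Under 7.4 a subject needs new proteinuria and a doubling of ACR. Read line by line, Table 15-1 is met by an ACR of 30 mg/g or more, whatever the baseline value was.

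The exclusion criteria bar eGFR below 60 and dipstick hematuria at screening, but not albuminuria or proteinuria. Protocol 5.3 aims for at least 30 % of subjects in each glycemic stratum, T2DM included. Some subjects may therefore meet the ACR line before the first dose and again, unchanged, at the first urinalysis after it.

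Kidney injury is a question the trial set out to examine: Protocol 6.5.6 gives it as the reason for the renal biomarkers, and SAP 2.8.1.1 lists impaired renal function as a pre-defined risk. Background events in arms of 36 or 72 subjects would blur a real difference.

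**Working it through.** The documents state no renal event rate, so there is no figure to reproduce. The arm sizes do reproduce: 432/12 = 36, and 2 × 36 = 72, as in Protocol 5.2.

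**Step 1. The criteria side by side**

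| SAP Table 2-8 / Protocol Table 15-1 | Link to baseline | Confirmation in the table | Protocol 7.4 |
|---|---|---|---|
| Creatinine +25–49 % | yes | an action | ≥ 25 %, confirmed, normal hydration |
| Creatinine +50 % or more | yes | follow-up only | same line as above |
| New dipstick proteinuria | yes (new) | an action | required, together with ACR doubling |
| ACR or PCR 2-fold or more | a change; reference not named | an action | ACR doubling only, as confirmation |
| ACR ≥ 30 mg/g | none | an action | absent |
| PCR ≥ 150 mg/g | none | an action | absent |
| New dipstick hematuria | yes (new) | none | new onset |

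Four criteria are tied to baseline, one is a change with its reference unnamed, and two are absolute: 4 + 1 + 2 = 7. Confirmation is part of the definition in 7.4 but only an action in the tables. Normal hydration appears only in 7.4.

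**Step 2. Subjects who could meet the ACR line unchanged**

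Assumptions, none from the documents: prevalence of baseline ACR ≥ 30 mg/g of 10–30 % in T2DM and 3–8 % in the others; T2DM share 30–40 % (Protocol 5.3 gives only the 30 % floor).

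Overall proportion = share × prevalence in T2DM + (1 − share) × prevalence in others.

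- Low: 0.30 × 0.10 + 0.70 × 0.03 = 0.051; 432 × 0.051 = 22.
- High: 0.40 × 0.30 + 0.60 × 0.08 = 0.168; 432 × 0.168 = 73.

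Per arm this is 1.8–6.0 of 36, or 3.7–12.1 of 72.

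**Step 3. What confirmation changes**

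Take ACR as lognormal with no true change and within-subject coefficient of variation CV (assumed), so s = √ln(1 + CV²). The chance that one value is at least double baseline is 1 − Φ(ln 2/(s√2)). For CV 30 %, s = 0.294 and the chance is 4.75 %. SAP 2.8.3 gives two post-baseline urinalysis visits in Epoch 3 (205 and 299). Simulation over both, sharing one baseline value, gave:

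| CV | Any single value | Confirmed by a repeat |
|---|---|---|
| 20 % | 1.3 % | 0.1 % |
| 30 % | 8.3 % | 2.0 % |
| 40 % | 17.0 % | 5.7 % |
| 60 % | 29.7 % | 13.1 % |

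Whether confirmation is needed therefore matters to the count. Requiring new dipstick proteinuria as well, as 7.4 does, would lower these figures further; that was not modelled.

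**Step 4. Effect on a comparison**

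Suppose true new-event rates of 2 % and 8 % (assumed), a ratio of 4.0. A background b in both arms turns a rate p into b + (1 − b)p.

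- b = 5 %: 6.9 % and 12.6 %, ratio 1.83.
- b = 10 %: 11.8 % and 17.2 %, ratio 1.46.

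The difference shrinks little (6.0 to 5.7 and 5.4 percentage points), but the ratio falls sharply.

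**The case against.** A reader might infer that the whole table ignores baseline. It does not: the creatinine and dipstick rows are tied to baseline and the 2-fold line is a change. A reader might also infer that the SAP departs from the protocol. It does not: Table 2-8 repeats Table 15-1, which 7.4 cites, so the mismatch lies inside the protocol and the SAP inherits it.

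Nor do the documents show that stable albuminuria and chance variation *are* counted. SAP 2.8.7 never says that Table 2-8 is applied by program to laboratory values, whereas SAP 2.8.6 does apply its liver criteria that way. The renal section mentions event overview, pathology and imaging data, and Protocol Table 15-1 has sites document events in the eCRF, which suggests investigator-reported events. A repeat measurement is a listed action for the proteinuria block. These points stand and limit the claim to *can be counted*. They do not remove it, because an investigator following Table 15-1 as written may report an unchanged ACR of 30 mg/g or more, and repeating a stable value only confirms it.

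The urine block could also be read as joint conditions, which would come close to 7.4. No and/or rule is stated, however, and a strict reading that needs every line could not be met from scheduled tests, since PCR is not scheduled.

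Finally, renal safety does not rest on this table. Laboratory changes from baseline and shift tables (SAP 2.8.3), adverse events of special interest (2.8.1.1) and substudy biomarkers (2.12) stand beside it. The table is also split by criterion, so an excess driven by ACR should show in its own category. That lowers the stakes, and it would be wrong to call the table unreadable.

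**Conclusion.** The concern holds in a limited form. Protocol 7.4 and Table 15-1 / SAP Table 2-8 give different definitions of the same renal event. The problem is confined to the two absolute thresholds and to whether confirmation, and normal hydration for creatinine, belong to the definition.

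Unchanged baseline albuminuria can enter the SAP 2.8.7 summary. The size, about 5–17 % of subjects, rests on assumed prevalences, on the ACR line counting alone, and on such cases being recorded as events. In practice it bears on ACR, since no PCR is scheduled. The background would be expected in all arms, placebo included, so the risk is a blurred comparison rather than a false signal. The table is descriptive, and the primary analysis and its power are untouched.

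**What to change.** **Reconcile the definitions.** Protocol 7.4, Protocol Table 15-1 and SAP Table 2-8 should carry one definition, including the and/or logic of the urine block and the place of confirmation and hydration. PCR serves as trigger and resolution measure although only ACR is scheduled; the passages must be brought into line, with the clinical content left to the sponsor.

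**In SAP 2.8.7:**

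- State whether events come from the eCRF or from laboratory values.
- Count a urine event as treatment-emergent only if the criterion was not already met at the Visit 201 baseline. SAP 2.8.4 already restricts notable vital signs to new or worsening values.
- Show subjects who already met a criterion at baseline separately.
- Present confirmed and unconfirmed events separately.
- State which baseline applies in Epoch 4. SAP 2.1.1 moves it to the last Epoch 3 measurement for Epoch 4-only analyses, so a doubling would be measured from a value that may already be raised.

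**Cost.** Clarified wording in one protocol section, one appendix table and one SAP section, minor extra programming, and somewhat lower event counts. No new samples are needed for the ACR comparison, since urinalysis is already collected at Visit 201.
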